Post-intensive care syndrome (PICS) is a common consequence of an intensive care unit (ICU) stay and can last up to 5 years.[1–3] The family members are often affected, reporting diminished quality of life and mental health related quality of life.[4] About 80% of family members become informal carers and 33% of families

see a significant reduction of income the first 6 months after discharge.[5] The extent to which these problems will be modified by the pandemic and coronavirus disease 2019 (COVID-19) remains unknown.

If under normal circumstances, an ICU stay has detrimental effects, the pandemic added two extra factors. Firstly, a rapid and exponential increase in acute care bed capacity might have affected the quality of care delivered by spreading too thin highly skilled healthcare staff. Secondly, COVID-19 involves a new disease with great uncertainties regarding treatment, prognosis and long-term effects. Early reports suggest that 64% of patients who were discharged from ICU after severe COVID-19 have at least one symptom of PICS at 6 months after discharge[6] and 32% had anxiety or depression symptoms,[7] which suggests these patients will have similar impairments to what has been reported for other ICU survivors previously.[8,9] Additionally, infection control protocols meant that healthcare staff had to wear personal protective equipment and family visiting was restricted.[10] These factors add another layer of potential negative effects due to challenges in communication with patients and their family members. Therefore, we hypothesize that the prevalence and severity of mental, physical, and cognitive impairments will be higher in patients treated in periods of higher bed occupancy and those who had severe COVID-19. In the case of family members, we expect that the experience of having a next of kin in the ICU during pandemic would be stressful and traumatic, but those with social support will cope better. In the case of staff members, their experiences will vary greatly depending on their profession and workplace, but we expect places with a more open/ less hierarchical structure to have coped better with the increase in demand.

The primary objective of this study is to compare the trajectory of mental, physical and cognitive impairments at ICU discharge, 3 and 6 months of mechanically ventilated adult patients who survived an ICU stay due to severe COVID-19 or other causes, during the pandemic. Secondary objectives are:

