- To compare the disability, quality of life and survival rate at ICU discharge, 3 and 6 months of patients who were admitted to ICU due to severe COVID-19 or other causes during high and low bed occupancy in the pandemic;
- To describe the sedentary behaviour and physical activity levels in a sample of ICU survivors during the COVID-19 pandemic using a one-week actigraphy protocol;
- To explore the psychological and emotional experiences reported by family members/next of kin of patients admitted to the ICU during the COVID-19 pandemic;
- To explore the emotional, intellectual, physical and administrative challenges faced by the participating ICU staff during the COVID-19 pandemic;
- To evaluate the feasibility of the follow-up from ICU discharge to 3 and 6 months during the pandemic.

METHODS

Study design and setting

The “Impact on Mental, Physical, And, Cognitive functioning of Critical care Time due to COVID-19” (IMPACCT-COVID19) is a prospective, multicentre, cohort study in seven Chilean academic medical-surgical ICUs. This study also involves a

qualitative component including semi-structured interviews with family members/next of kin of ICU survivors and with ICU staff from the participating centres. Participating sites are four public and three private hospitals comprising a pooled bed capacity of about 200 ICU beds for both COVID-19 patients and patients admitted for other causes. The IMPACCT-COVID19 study started in October 2020. Data collection is planned until November 2021 to achieve completion of the study in February 2022.

Study population and eligibility criteria

Adult patients (≥ 18 years old) who are mechanically ventilated for at least 48 hours in one of the participating ICUs and do not meet any of the exclusion criteria (**Table 1**) will be invited to participate.

Table 1. Exclusion and stopping follow-up criteria

Exclusion criteria	Rationale
Unable to walk independently 2 weeks prior to ICU admission (with or without a gait aid)	Potential confounding factor
S5q < 5 or CAM-ICU positive within 72 hours after ICU discharge	Unable to evaluate
Patient who do not understand or speak Spanish	Unable to evaluate
Patient unable to communicate verbally	Incomplete assessment data
Burn or severe trauma as admission diagnosis	Incomplete assessment data
Any neurological disorder (i.e. spinal cord injury, stroke and brain tumours) as admission diagnosis	Potential confounding factor

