Transferred to a non-participating study centre before ICU discharge assessment	Unable to evaluate
Recent prolonged hospital stay (extended by more than 3 months)	Potential confounding factor
Criteria to stop follow-up	
Re-admission after being ICU discharged	Potential confounding factor
Withdrawal of consent	Incomplete assessment data
Death before 3 or 6 months from ICU discharge	Incomplete assessment data

ICU, intensive care unit; s5q, simple 5 questions scale; CAM-ICU, Confusion Assessment Method for the Intensive Care Unit

Procedure

The planned flow of participants throughout the study is presented in **Figure 1**.

Daily, patients will be screened to identify those who could potentially be discharged from the ICU. Each site coordinator, which is a clinician physiotherapist responsible for the site, will check that the patient is delirium-free (CAM-ICU negative) and cooperative (i.e. using 5 standardised questions: open [close] your eyes; look at me; open your mouth and stick out your tongue; nod your head; raise your eyebrows when I have counted up to five[11]) within 72 hours from ICU discharge. Every patient deemed eligible will be invited to participate and will receive verbal and written information about the study. Patients will be assessed at ICU discharge (T1, defined by the point between medical decision of discharge until 72 hours after), 3 months (T2) and 6 months after ICU discharge (T3). Fifty-eight physiotherapists were trained for the assessments at ICU discharge, which included in-person measurements and self-administered questionnaires. Physiotherapists had to be working in one of the participating ICUs at the time of the training. Training for standardising T1 assessments was delivered by experienced physiotherapists and researchers (ACM, CMO and FGS). For the follow-up assessments (T2 and T3), patients will be contacted via email or telephone to schedule a phone call evaluation performed by trained interviewers.

Baseline data collection

After the patient agreed to participate and signed the informed consent form, the following baseline data will be collected from the patient clinical records: age, gender, body mass index (BMI), highest educational level achieved (no formal

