education, primary school, secondary school, undergraduate or postgraduate), admission diagnosis, Charlson Comorbidity Index, duration of mechanical ventilation, length of hospital stay before ICU admission, ICU length of stay, number of intubations and the maximum level of organ system support received.[12]

Measurement Outcomes

The assessment points and measurement instruments are presented in **Table 2**. Measurement instruments were selected according to the recommended Core Outcome Measurement Set for critical illness survivors.[13,14]

Table 2. Schedule of enrolment and follow-up of the IMPACCT-COVID19 study

	Study period		
	Enrolment		Follow-up
	ICU	3 months from enrolment	6 months from enrolment
Eligibility screening			
Inclusion and exclusion	X		
Invitation to participate			
Informed consent	X		
Patient characteristics			
Age, gender, BMI	X		
Data related to hospitalisation			
Diagnosis, MV days, ICU LOS	X		
Maximum level of organ system support	X		
Pre-admission health and functioning			
Charlson Comorbidity Index	X		
Educational level	X		
Employment status	X	X	X
Clinical Frailty Scale	X	X	X
Physical functioning			
MRC Sum Score	X		
FSS-ICU	X		
Cognitive functioning			
MoCA blind	X	X	X

Mental functioning			
IES-R	X	X	X
HADS	X	X	X
Disability and quality of life			
WHODAS 2.0	X	X	X
EQ-5D-3L		X	X
Sedentary behaviour and physical activity			
Actigraphy			X
GPAQ			X
Survival rate	X	X	X

ICU, intensive care unit; BMI, body mass index; MV, mechanical ventilation; LOS, length of stay; FSS-ICU, Functional Status Score for the Intensive Care Unit; MRC, Medical Research Council; MoCA, Montreal Cognitive Assessment; IES-R, Impact of Event Scale Revised; HADS, Hospital Anxiety and Depression Scale; WHODAS, World Health Organization Disability Assessment Schedule; EQ-5D-3L, European Quality of Life Health Questionnaire 5 domains; GPAQ, Global Physical Activity Questionnaire

When available, we used the Chilean version of each instrument, otherwise, the validated version in Spanish. Trained physiotherapists will take an estimated maximum time of 70 minutes to perform the assessment at ICU discharge (T1). A trained interviewer will take an estimated maximum time of 20 minutes to apply the questionnaires by telephone at 3 (T2) and 6 months (T3) after ICU discharge.

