The primary outcome measure is disability assessed at 6 months after ICU discharge using the World Health Organization Disability Assessment Schedule 2.0 (WHODAS 2.0) which is recommended for critical illness survivors.[8] The WHODAS 2.0 is a self-reported disability questionnaire based on the International Classification of Functioning, Disability, and Health (ICF). It includes 36 questions, organised under six domains (cognition, mobility, self-care, getting along, life activities and participation). Each question must be answered based on the perceived difficulty for performing activities using a 5-point scale (none, mild, moderate, severe and extreme).[15] We will use the Spanish version freely

available at <https://apps.who.int/iris/handle/10665/170500>.[16] The estimated response time ranges from 5 to 10 minutes when evaluated in-person at ICU discharge and 10 to 20 minutes when evaluated by telephone at 3 and 6 months after ICU discharge.

Secondary outcomes measures

Clinical Frailty Scale

The Clinical Frailty Scale (CFS) is a clinical judgment based tool developed for the Canadian Study of Health and Aging to evaluate the degree of frailty in elderly patients.[17] Currently, it is also used for critically ill patients.[18] The CFS evaluates specific domains including physical functioning, activities of daily living (ADL), instrumental ADL, assistance for personal care, comorbidities, and cognition to generate a frailty score using a 9-point scale ranging from 1 (very fit) to 9 (terminally ill). A score greater than 4 is considered fragile.[17] We will use the Spanish version and recommended training material by the developers at the Dalhousie University.[17,19] The estimated scoring time ranges from 1 to 5 minutes evaluated in-person at ICU discharge considering the status 2 weeks before the onset of symptoms.

Medical Research Council Sum Score (MRC-SS)

Limb muscle strength will be assessed using the MRC-SS, which consists in a standardised examination of six muscle groups bilaterally (i.e. shoulder abduction, elbow flexion, wrist extension, hip flexion, knee extension and dorsiflexion).[20] All muscle groups are scored using a 6-point scale between 0 and 5 (0 = no visible /

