the rest areas to capture a wider population. We will recruit medics, nurses, healthcare assistants and physiotherapists that normally work in an ICU and have patient-facing clinical duties for more than 96 hours during the pandemic. The invitation to participate will lead to a google form containing information about the study and a short script that constitutes the informed consent. From the list of volunteers, we will purposely sample three professionals per clinical group aiming to maximise variation regarding years of experience and centre where they work. We expect a minimum of 40 interviews, but we will continue recruitment until data saturation is achieved. Interviews will be conducted online or over the phone. Participants will be asked for verbal consent before starting the interview, which will be recorded for later transcription verbatim. Interviews will be semi-structured covering five main topic areas: preparation before the pandemic; intellectual, physical and emotional challenges during the pandemic; and learning for future events.

Follow-up feasibility

The consent rate will be collected, calculating the number of patients who agreed to participate divided by the number of patients who meet selection criteria, expecting a consent rate of > 70%. [39] The feasibility over-time during the follow-up will be measured as cohort retention rate, considering the number of patients who can be contacted and evaluated at 3 and 6 months. [40,41] The reasons for the lack of assessments will be recorded individually.

Sample size calculation

All patients meeting the eligibility criteria discharged from ICU between October 2020 and April 2021 (due to funding constraints) will be invited to participate.

Based on bed capacity and patient flow from previous years, we estimated that 20 to 30 mechanically ventilated adult patients are discharged monthly from each centre. This means the sampling universe ranges from 840 to 1260 patients.

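### Stopping follow-up at re-admission as a confounder withholds the 6-month primary outcome from patients selected by an event that follows the exposures

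*Combined protocol and SAP*

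**What the plan says.** Table 1 of the combined protocol and SAP has a block of criteria for ending follow-up. One is "Re-admission after being ICU discharged", with possible confounding as its rationale; the other two are withdrawal of consent and death. The available text gives no destination (ICU or hospital), cause or time window for re-admission.

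The Introduction hypothesises that impairments "will be higher in patients treated in periods of higher bed occupancy and those who had severe COVID-19". The first secondary objective compares disability and other outcomes between COVID-19 and other causes of admission "during high and low bed occupancy in the pandemic". Under Measurement Outcomes, "The primary outcome measure is disability assessed at 6 months after ICU discharge", using WHODAS 2.0.

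Quantitative analysis specifies a longitudinal multilevel regression. It states no method for missing outcomes, no sensitivity analysis, and no handling of patients stopped by this rule. Follow-up feasibility says that "The reasons for the lack of assessments will be recorded individually".

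**The concern.** A confounder must not be a consequence of the exposure. Cause of admission and bed occupancy belong to the index stay (occupancy at discharge, in the sample size section), so both precede any re-admission. Re-admission can therefore be a step between exposure and disability, or an outcome in itself. The hypothesis that strained care and COVID-19 worsen recovery makes it a plausible step.

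Of the three stopping criteria, re-admission is the only one after which the patient may be both alive and willing to answer. Here the plan creates missing data by choice. The people affected are selected on a health event after discharge and are probably sicker, although the documents hold no data on that.

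The level of 6-month disability among survivors and its comparison between groups are both at stake. There are two smaller consequences. The retention rate counts patients who are contacted and assessed, so the rule can lower it among people who could have been reached. Under Ethical considerations, information on rehabilitation options depends on the 3- or 6-month WHODAS result, which stopped patients will not have.

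**Working it through.** **Plan's own figure.** The sample size section expects 550 recruited, 25% lost by 3 months and a further 30% by 6 months: 550 × 0.75 = 412.5 (stated as 413), and 413 × 0.70 = 289.1 (stated as 289). This reproduces. Total planned loss is 1 − 289/550 = 47.5%, not split by cause, so the text does not show whether re-admission is inside it.

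**Inputs.**
- P, true prevalence of any disability: 0.40 in low-demand and 0.64 in high-demand periods (sample size section), a difference of 24 points.
- r, share re-admitted among those otherwise reachable at 6 months: 5-15%, assumed.
- p, share of re-admitted patients who are disabled: 70-85%, assumed.

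**Scores withheld**, if 289 would be reachable without the rule: 0.05 × 289 = 14 to 0.15 × 289 = 43.

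**Prevalence.** With re-admitted patients removed, the observed value is (P − r·p)/(1 − r), so the shortfall is r(p − P)/(1 − r).

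| P | Smallest shortfall | Largest shortfall |
|---|---|---|
| 0.40 | 0.05 × 0.30/0.95 = 1.6 points | 0.15 × 0.45/0.85 = 7.9 points |
| 0.64 | 0.05 × 0.06/0.95 = 0.3 points | 0.15 × 0.21/0.85 = 3.7 points |

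**Contrast, same p in both groups.**

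| r low / high demand | p | Observed low vs high | Difference |
|---|---|---|---|
| 5% / 15% | 0.85 | 37.6% vs 60.3% | 22.7 |
| 15% / 5% | 0.85 | 32.1% vs 62.9% | 30.8 |
| 5% / 15% | 0.70 | 38.4% vs 62.9% | 24.5 |
| 15% / 5% | 0.70 | 34.7% vs 63.7% | 29.0 |
| 10% / 10% | any | – | 24/0.9 = 26.7 |

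**Contrast, with re-admitted patients keeping the 24-point gap.** A 24-point gap does not fit inside 70-85%, so the low-demand value has to drop below that range or the high-demand value rise above it.

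| p low / high demand | r 5% / 15% | r 15% / 5% | Equal r |
|---|---|---|---|
| 0.46 / 0.70 | 23.3 | 24.7 | 24.0 |
| 0.61 / 0.85 | 21.4 | 26.6 | 24.0 |
| 0.70 / 0.94 | 20.3 | 27.7 | 24.0 |

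Wider assumptions move it further: r of 10% and 30% with p = 0.90 gives 34.4% vs 52.9%, a difference of 18.4 points.

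**What the planned model can recover.** All these figures are for complete cases. A patient re-admitted before 3 months has only the ICU-discharge WHODAS; one re-admitted between 3 and 6 months also has the 3-month score. The multilevel model can use those scores, and removes the bias only if the 6-month value is missing at random given them. No score after re-admission exists with which to check that.

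**The case against.** The strongest defence is that the rule is deliberate and disclosed. The study concerns the consequences of an ICU stay. If re-admission means ICU re-admission, which is a natural reading in this cohort, a second stay is further exposure, perhaps at a different occupancy, and a score 6 months after the first discharge mixes the two. This is a legitimate target even if confounding is the wrong word for it. But it can be met by excluding re-admitted patients at analysis, so it does not require leaving their scores uncollected.

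Several limits do stand:
- Figure 1 is not shown, so the lack of a definition can be asserted only for the available text.
- Both assumed rates lack a source in the documents.
- The figures describe complete cases, not the planned model. They use low versus high demand, whereas the primary objective compares COVID-19 with other causes.
- Many baseline measures, and 3-month scores for later re-admissions, will exist and could support adjustment under missing at random or a sensitivity analysis that departs from it. The plan specifies neither.
- Deaths come from the civil registry, so survival can still be known after follow-up stops.

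The planned 47.5% loss is no answer: it allows for reduced numbers, and recruiting more patients does not cure selective loss.

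**Conclusion.** The concern holds. Re-admission follows both exposures and cannot confound them. Ending follow-up there withholds the primary outcome from a group selected on a later health event, and the plan offers no remedy beyond a model that depends on an assumption it cannot test.

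If re-admitted patients are more disabled at 6 months, disability among survivors is understated. The contrast may be overstated, understated or unchanged, depending on how re-admission, and disability after it, are spread over the groups. Under the 5-15% and 70-85% assumptions the effect runs from negligible to about 8 points of prevalence. The reasoning is firm; the magnitude is unknown. This is a change that should be made, not a flaw that invalidates the study.

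**What to change.** Remove re-admission from the criteria to stop follow-up for every assessment still to be made, and continue the 3- and 6-month calls counted from the index ICU discharge. Define re-admission as ICU or hospital, record its date, and report it by group. Make the analysis that includes re-admitted patients the main one and their exclusion a sensitivity analysis. Report scores already missed under the rule, by group and time point. For those, a sensitivity analysis that shifts the imputed values away from missing at random would show how much the result depends on them; it needs no further contact with patients.

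The cost is a protocol amendment, possibly reviewed by each site's ethics committee, and a check that consent covers calls after re-admission. Some calls will need rescheduling around a second stay. Interviewer time should be budgeted realistically. The plan says "A trained interviewer will take an estimated maximum time of 20 minutes to apply the questionnaires by telephone", yet WHODAS alone takes "10 to 20 minutes when evaluated by telephone at 3 and 6 months", and the stated times add up to 25-38 minutes: WHODAS 10-20, MoCA 5, HADS 2-5, IES-R 6, EQ-5D 2.

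The benefit is limited by time. Eligible discharges ran from October 2020 to April 2021, and "Data collection is planned until November 2021". Only calls still due can be saved; scores already missed cannot be recovered.

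### Psychiatric history is neither an exclusion nor a baseline item, and pre-ICU cognition enters only through composite scores, so the planned data cannot adjust the COVID-19 versus other-cause comparison of mental outcomes, and only weakly that of cognitive outcomes, for prior illness

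*Combined protocol and SAP*

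**What the plan says.** The primary objective in the Introduction is to "compare the trajectory of mental, physical and cognitive impairments at ICU discharge, 3 and 6 months" between survivors of severe COVID-19 and survivors of other critical illness. Two of those three domains are mental and cognitive.

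What the plan does about status before the ICU:

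- **Exclusions (Table 1).** Poor prior mobility excludes: "Unable to walk independently 2 weeks prior to ICU admission (with or without a gait aid". The rationale given is possible confounding. Brain disease excludes only when it is the reason for admission: "Any neurological disorder (i.e. spinal cord injury, stroke and brain tumours) as admission diagnosis". The screen "S5q < 5 or CAM-ICU positive within 72 hours after ICU discharge" concerns the patient's state around discharge, not history.
- **Baseline items (Baseline data collection).** The source is the chart: "the following baseline data will be collected from the patient clinical records". After demographics, body mass index and education, the list runs "admission diagnosis, Charlson Comorbidity Index, duration of mechanical ventilation, length of hospital stay before ICU admission, ICU length of stay, number of intubations" and ends with organ support.
- **Table 2.** The block headed "Pre-admission health and functioning" holds the Charlson index, educational level, employment status and the Clinical Frailty Scale.
- **Clinical Frailty Scale (Secondary outcomes measures).** Cognition is one of several domains behind a single score from 1 to 9. The discharge rating refers to the patient's status two weeks before symptoms began.
- **HADS, IES-R and MoCA-blind.** Each is first administered at ICU discharge and repeated at 3 and 6 months.
- **Quantitative analysis.** Longitudinal multilevel regression is planned. No adjustment covariate is named.

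**The concern.** The two groups are formed by cause of admission, not by randomisation, so nothing in the design makes earlier depression, anxiety, post-traumatic stress or cognitive impairment equally common in them. These conditions can reasonably be expected to predict the scores on which the groups are compared. The plan recognises this kind of problem for prior walking ability and deals with it by exclusion. It makes no corresponding provision for mental illness and only an indirect one for cognition. A patient with treated depression, or with known cognitive impairment, who is ventilated for pneumonia or sepsis can be enrolled, provided the discharge screens are passed, and the history goes unrecorded except as far as the frailty or comorbidity score reflects it.

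Two things are at stake. If prior history is unevenly distributed, part of any difference between the groups in mental or cognitive outcome reflects illness that predates the ICU. Even if it is evenly distributed, the absolute prevalence of impairment attributed to the ICU stay includes cases that were already there. As planned, the data could not show which situation applies.

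**Working it through.** The plan states no figure on this point, so there is none to reproduce. The check is a comparison of sections, followed by an illustration of size.

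**1. Is prior status available anywhere in the planned data?**

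| Pre-ICU status | Exclusion (Table 1) | Baseline list | Table 2 pre-admission block |
|---|---|---|---|
| Walking ability | Yes | – | Within the frailty score |
| Psychiatric diagnosis or treatment | No | No | No item described as covering it |
| Cognitive impairment | Only if a neurological disorder is the admission diagnosis | No dedicated item; Charlson components not listed | One domain within the frailty score; Charlson components not listed |

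**2. Can the ICU-discharge scores stand in?** No. They follow the critical illness and the ICU stay. A discharge HADS score mixes prior symptoms with the effect under study. Conditioning on it does not recover pre-ICU status and may remove part of that effect.

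**3. How large could the bias be?** For an unmeasured yes/no history that multiplies outcome risk by k in both groups:

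bias factor = [1 + p_COVID × (k − 1)] / [1 + p_other × (k − 1)]

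The observed risk ratio is the true one times this factor. The inputs are assumptions, because the documents give none: history in 10% to 30% of each group, k from 2 to 3.

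| p_COVID | p_other | k | Calculation | Factor |
|---|---|---|---|---|
| 0.10 | 0.30 | 3 | 1.20 / 1.60 | 0.75 |
| 0.10 | 0.30 | 2 | 1.10 / 1.30 | 0.85 |
| 0.10 | 0.20 | 2 | 1.10 / 1.20 | 0.92 |
| 0.20 | 0.20 | any | equal terms | 1.00 |
| 0.20 | 0.10 | 2 | 1.20 / 1.10 | 1.09 |
| 0.30 | 0.10 | 2 | 1.30 / 1.10 | 1.18 |
| 0.30 | 0.10 | 3 | 1.60 / 1.20 | 1.33 |

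A true risk ratio of 1.0 could therefore appear as anything from 0.75 to 1.33.

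**4. A sense of scale.** The HADS row of Table 3 uses a risk ratio of 1.8 for pandemic against non-pandemic conditions. That is not a COVID-19 versus other-cause effect and is borrowed here only as a yardstick. A true 1.8 would appear as 1.8 × 0.75 = 1.35 up to 1.8 × 1.33 = 2.40. To explain 1.8 away entirely, the history would need a risk ratio of at least 1.8 + √(1.8 × 0.8) = 3.0 with both group and outcome. The bias could thus distort an effect of that size materially, but would be unlikely to create all of it.

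**The case against.** **Cognition is not wholly missing.** A reader might infer that nothing about prior cognition is collected. That goes too far. The discharge rating of the Clinical Frailty Scale refers to the period before illness and includes cognition, and the Charlson index may carry a relevant component, since the documents do not list its parts. Education is also recorded, and the discharge screens remove some of the most impaired patients. This stands, and it makes the cognitive half of the point weaker than the mental half. It does not close the gap: one composite grade cannot isolate cognition, and no model is committed to using it.

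**The gap can be repaired.** A reader might also infer that no later step could correct the comparison. The documents do not support that. Baseline data come from clinical records, so history can be retrieved for patients already enrolled. The limitation belongs to the data set as planned.

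**The bias is conditional.** With equal prevalence the factor is 1.00, and its direction is unknown. Any claim that the COVID-19 effect will be diluted, or that a particular planned effect will shrink, goes beyond the documents. The risk ratio of 1.6 in Table 3 belongs to WHODAS 2.0 disability under pandemic against non-pandemic conditions, so it cannot be used as the expected mental-health difference between the groups.

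**Trajectories and the primary outcome.** Stable prior differences partly cancel in change from discharge, and the calculation above treats a single time point. That is fair. But the plan also analyses HADS and IES-R as categories at each time, where levels matter, and a post-exposure start does not isolate prior status. The primary outcome is WHODAS 2.0 at 6 months, and the three instruments most affected are secondary. WHODAS 2.0 does contain cognition, getting-along and participation domains, so it is exposed less directly.

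**Missing covariates generally.** No adjustment set is specified even for items already collected. That is a related gap, but naming covariates would not supply a psychiatric variable that is not collected.

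**Conclusion.** The point holds in a limited form. Psychiatric history is neither excluded nor collected, pre-ICU cognition is available only inside composite measures, and the relevant scales start after the exposure. Following the plan as written leaves the comparison in the primary objective unadjustable for prior mental illness and only weakly adjustable for prior cognitive impairment.

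The size is uncertain. The range of 0.75 to 1.33 rests wholly on the assumed prevalences and risk multiplier, on the same multiplier in both groups, and on no other confounding. The documents establish neither an imbalance nor its direction. What they do establish is that the planned data could not reveal one. The change is worth making because it costs little and bears on two of the three domains in the primary objective.

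**What to change.** 1. Add two yes/no items to the chart extraction under Baseline data collection and to the pre-admission block of Table 2: psychiatric diagnosis or treatment before admission, and diagnosed cognitive impairment or dementia before admission. Take the second from the Charlson record if it is already there.
2. Back-fill both from the same clinical records for patients already enrolled, and report both by group.
3. In Quantitative analysis, name the covariates: psychiatric history in the HADS and IES-R models; cognitive history, the pre-illness Clinical Frailty Scale and education in the MoCA-blind model; both history items in a sensitivity analysis of WHODAS 2.0.
4. State that records under-report prior mental illness and that residual confounding will remain. If back-filling proves incomplete, report a bias analysis of the kind shown above.

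Cost: two fields in an extraction that already takes place, a retrospective chart check and a few model terms. No new visit or patient procedure is needed. Because each site's ethics committee approved the protocol, a minor amendment for the added sensitive data may be required.
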